5.3 Schedule of Events

The overall trial plan is introduced in **Table 1** and further defined in the following sections.

Confidential Page 38 of 156

Table 1 Overall Trial Plan

	Screening Period				
Screening	14 days within first dose of Pan-HER				
	Treatment Period				
Treatment Allocation	The allocated dose and schedule of Pan-HER will depend upon cohort assignment				
	and will be confirmed by Sponsor or designee on the Screening and Allocation Form .				
Pan-HER	Pan-HER will be initiated on C1/D1 and, based on cohort assignment, will be				
	administered either Q1W or Q2W to separate dose-escalation cohorts of patients by				
	IV infusion in cycles of treatment:				
	• Q1W: Dosing on Day 1, 8, 15, and 22 of each 28-day cycle (±2 days)				
	Q2W: Dosing on Day 1 and 15 of each 28-day cycle (±2 days)				
	The duration of infusion will be (effective with Amendment 5):				
	• Minimum of 4 hours (+10 min) for all infusions. Titrated rate increases during				
infusions, and infusion duration reductions after C1/D1, will no longer be allowed					
	For Part 1 of the trial, Pan-HER will be administered following delivery of intensive				
	prophylaxis, as defined herein, on a mandatory basis to reduce the risk of IRRs and				
	oropharyngeal mucositis.				
	For Part 2, IRR and oropharyngeal mucositis prophylaxis is mandatory during Cycle				
	1 and 2. If the patient is without evidence of IRRs or oropharyngeal mucositis after				
	Cycle 2, the Investigator may choose to withdraw related medications with				
	subsequent dosing. Gradual withdrawal of medications is recommended.				
Discontinuation of Pan-	Treatment will continue until unacceptable toxicity or other conditions preventing				
HER	further treatment, PD, termination of the trial, or patient's decision to withdraw.				
	End of Treatment				
End of Treatment Visit	Within 10 days after the decision to discontinue Pan-HER, an EOT Visit should be				
	performed.				
1 Manda Dallaman	Follow-up				
1-Month Follow-up	Follow-up continues until 1 month (30+7 days) after the last dose of Pan-HER. At				
Visit	that time, a 1M FUP Visit should be performed. This visit constitutes the end of trial				
D 2 ONL V	participation for the patient.				
Part 2 ONLY:	After the 1M FUP Visit, the Investigator will make every effort to obtain follow-up				

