Abbreviations (in alphabetical order): ADA, anti-drug antibody; C, Cycle; CT, computed tomography; D/d, day(s); DLT, dose-limiting toxicity; EOT, End of Treatment Visit; ECG, electrocardiogram; ECHO, echocardiogram; ECOG PS, Eastern Cooperative Oncology Group performance status; MRI, magnetic resonance imaging; MUGA, multi-gated acquisition; 1M FUP, 1-Month Follow-up Visit; PK, pharmacokinetic; (S)AE, (serious) adverse event

Confidential Page 45 of 156

- 1) The treatment period continues until the patient is withdrawn from Pan-HER
- 2) Applicable for Part 2 only: After the 1M FUP Visit, the Investigator will make every effort to obtain follow-up information on response assessment and/or OS every 2 months. Response assessment follow-up is required in the event of an ongoing SD, PR or CR at the 1M FUP Visit, until PD or another therapeutic intervention is initiated. Survival follow-up is required until death, withdrawal of consent, or termination of the trial. This continued follow-up does not require an in-person visit at the trial site, but may be obtained by collection of data/documentation
- 3) Informed consent may be obtained outside the 14-day screening period prior to C1/D1, but is recommended to be obtained no earlier than 4 weeks prior to the planned C1/D1
- 4) Screening assessments/baseline characteristics include demographics, medical history, tumor histology, mutation status, extent of disease, prior anti-cancer treatment etc.
- 5) DLT evaluation, Applicable for Part 1 only: DLTs are reported during Cycle 1 with final assessment 7 days after the last dose of Cycle 1 or prior to dosing on C2/D1
- 6) Does not need to be performed on C1/D1 if performed during screening \leq 7 days from C1/D1
- 7) In addition to the scheduled timepoints, an ECG should be performed in the event of cardiac symptoms
- 8) In addition to the scheduled timepoints, an ECHO/MUGA should be performed in the event of cardiac symptoms
- 9) Local laboratory results must be available and assessed prior to each Pan-HER infusion for all infusions during Cycle 1, and for every second infusion from Cycle 2 onwards. Refer to **Section 8.2.9** for further details
- 10) Complement sampling, Applicable for Part 2 only, will be done C1/D1 and in the event of an IRR. Refer to Section 8.2.10 for further details
- 11) CT or MRI imaging schedule and conditions, applying to all cohorts:

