8.2.3 Dose-Limiting Toxicities Evaluation (Part 1 Only)

For details about AEs meeting DLT criteria, refer to Section 9.5.

- Starting from the first dose of Pan-HER (C1/D1)
- Reported during Cycle 1 with final assessment 7 days after the last dose of Cycle 1 for Q1W dosing, 14 days after the last dose of Cycle 1 for Q2W dosing, or prior to dosing on Day 1 of Cycle 2 (C2/D1)

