9.5.2 Observation Period for Dose-Limiting Toxicities

The decision to dose-escalate will be based on close monitoring of safety during the observation period for DLTs, defined as the initial 28-day period (±2 days) from first treatment of Pan-HER (i.e., Cycle 1) and including 7 days of follow-up (Q1W dosing) or 14 days of follow-up (Q2W dosing) from the last dose of Cycle 1.

A minimum of 4 Pan-HER infusions (Q1W dosing) or 2 Pan-HER infusions (Q2W dosing) must have been administered at the assigned dose for a patient to have completed the DLT-observation period.

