- 2) **Applicable for Part 2 only:** After the 1M FLP Visit, the Investigator will make every effort to obtain follow up information on response assessment and/or OS every 2 months. Response assessment follow-up is required in the event of an ongoing SD, PR, or CR, at the 1M FLP Visit, until PD or another therapeutic intervention is initiated. Survival follow-up is required until death, withdrawal of consent, or termination of the trial. This continued follow-up does not require an in-person visit at the trial site, but may be obtained by collection of data/documentation.
- 3) Informed consent may be obtained outside the 14-day screening period prior to C1/D1, but is recommended to be obtained no earlier than 4 weeks prior to the planned C1/D1.
- 4) Screening assessments/baseline characteristics include demographics, medical history, tumor histology, mutation status, extent of disease, prior anti-cancer treatment etc.
- 5) DLT evaluation. **Applicable for Part 1 only:** DLTs are reported during Cycle 1 with final assessment 7 days after the last dose of Cycle 1, or prior to dosing on C2/D1.
- 6) Does not need to be performed on C1/D1 if performed during screening ≤ 7 days from C1/D1.
- 7) In addition to due scheduled timepoints, an ECG should be performed in the event of cardiac symptoms.
- 8) In addition to due scheduled timepoints, an ECHO/MUGA should be performed in the event of cardiac symptoms.
- 9) Local laboratory results must be available and assessed prior to each Pan-HER infusion for all infusions during Cycle 1, and for every second infusion from Cycle 2 onwards. Refer to Section 8.2.9 for further details.
- 10) Complement sampling. **Applicable for Part 2 only:** will be done C1/D1 and in the event of an ITR. Refer to Section 8.2.10 for further details.
- 11) CT or MRI imaging schedule and conditions, applying to all cohorts:

 - A CT/MRI performed within 28 days prior to C1/D1 can be used for evaluation of eligibility and as baseline scan, provided that the CT/MRI has been performed according to the clinical trial protocol requirements.
 - The first CT/MRI assessment for response is done at the end of Cycle 2 and thereafter repeated at the end of every second cycle (in the week prior to Day 1 of the next cycle)
 - In the event of suspected PD, a CT/MRI is to be performed as soon as possible
 - In the event of CR/PR, a confirmatory CT/MRI is to be performed 28 (+7) days after the first assessment of CR/PR

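### The Q2W schedule footnotes put the final DLT assessment at 7 days after the last Cycle 1 dose where the protocol and SAP text give 14, leaving a narrow gap for patients with no Cycle 2 Day 1 dosing visit

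*Protocol*

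**What the plan says.** - **Protocol 5.3.5, Table 3 (Q2W), footnote 5:** "DLTs are reported during Cycle 1 with final assessment 7 days after the last dose of Cycle 1 or prior to dosing on C2/D1". Footnote 5 of Table 2 (Q1W) is the same sentence.
- **SAP 7.2 (Q2W), footnote 5:** "DLTs are reported during Cycle 1 with final assessment 7 days after the last dose of Cycle 1", followed by the same Cycle 2 Day 1 (C2/D1) alternative.
- **Protocol 8.2.3:** separates the schedules. Q1W has 7 days; Q2W has the final assessment "14 days after the last dose of Cycle 1 for Q2W dosing". It also carries the C2/D1 alternative.
- **Protocol 9.5.2:** defines the observation period as "the initial 28-day period (±2 days) from first treatment of Pan-HER", "including 7 days of follow-up (Q1W dosing) or 14 days of follow-up (Q2W dosing) from the last dose of Cycle 1". SAP 3.2.4.1 gives the same window.
- **Table 3 grid:** marks DLT evaluation on Days 1, 3, 8, 15 and 22 of Cycle 1 and again at C2/D1. It marks none at the End of Treatment or 1-Month Follow-up visits.
- **Who counts as evaluable:** the only explicit completion condition in 9.5.2 is a minimum number of infusions at the assigned dose, two for Q2W. Protocol 10.2 and SAP 4.5 remove from the DLT Analysis Set only patients who failed to complete Cycle 1 for a reason other than drug toxicity.
- **How the result is recorded:** under SAP 3.2.4.1 the CRF holds a DLT Yes/No answer, the assessment date, a description and an AE reference.

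**The concern.** Cycle 1 DLT occurrence is the Part 1 primary endpoint, and four places in the two documents touch its closing date for Q2W patients without agreeing. The schedule table is a natural working reference for a site. Read on its own, the first half of its footnote allows a Q2W patient to be signed off one week after the Day 15 infusion.

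The C2/D1 alternative is tied to dosing, so it supplies no later assessment for a patient who is not dosed in Cycle 2, for example one who stops for progression on Day 23. That patient has had two infusions and so meets the infusion-count condition. The SAP describes no re-derivation of DLTs from AE records, so a No entered at Day 22 could pass unchanged into the DLT table. The last week of the defined window would then count as DLT-free without having been assessed.

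The Q2W cohorts are not a small part of the trial: at Amendment 6 they held 3 + 7 + 3 = 13 of the 19 patients entered (protocol 3.2.4.1).

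**Working it through.** **Inputs.** Dosing days come from protocol 5.3, Table 1: Q1W on Days 1, 8, 15 and 22; Q2W on Days 1 and 15. Follow-up lengths come from 8.2.3 and 9.5.2 and from Table 3 footnote 5.

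**Formula.** Elapsed days observed = (day of last Cycle 1 dose − 1) + follow-up days.

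**The plan's own figure.**
- Q1W, 7 days: (22 − 1) + 7 = 28.
- Q2W, 14 days: (15 − 1) + 14 = 28.

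Both reproduce the 28-day window of 9.5.2, with the final assessment on Day 29, which is C2/D1. So for Q2W the two alternatives in 8.2.3 fall on the same day.

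**The footnote's 7-day alternative under Q2W.**
- (15 − 1) + 7 = 21 elapsed days, final assessment on Day 22.
- Missing from the window: (28 − 21)/28 = 7/28 = 25%.
- Missing from follow-up after the second infusion: 7/14 = 50%.
- With the Day 15 dose given two days early or late (Day 13 or 17), the branch ends at 19 or 23 elapsed days. Against 28 days that is 9/28 = 32% or 5/28 = 18% missing.

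Under Q2W the footnote's two alternatives are a week apart; under Q1W they coincide. That, and the identical sentence in Table 2, suggest carry-over of the Q1W text. This is inference, though protocol 21.3 does record that 8.2.3 and 9.5.2 were changed to 14 days when Q2W was introduced.

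**Which patients are affected.**

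| Q2W patient | DLT evaluation after Day 22 | Window missing |
|---|---|---|
| Reaches C2/D1 | Yes, on the Table 3 grid | None |
| Misses the second infusion, not from toxicity | Not needed; replaced (6.4.1) and outside the DLT set | Not applicable |
| Misses the second infusion because of toxicity | Stays in the DLT set; DLT criterion 7 applies if Grade 3 or higher | Not the gap at issue |
| Has both infusions, no C2/D1 dosing visit | None scheduled | Up to 7 of 28 days |

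**Upper-bound illustration only.** Assume a constant DLT hazard, every Q2W patient closed at Day 22 and every later DLT missed. None of this is in the documents. A true 28-day rate of 33% would be seen as 1 − 0.67^(21/28) = 25.9%. Under the rules of protocol 7.1.3.2, P(escalate) = (1 − p)³ + 3p(1 − p)⁵, which is 43% at p = 0.33 and 58% at p = 0.259. For true rates of 20% and 50% the same steps give 71% to 81% and 17% to 30%.

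**The case against.** The case against making much of this is strong, and most of it stands.

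- The footnote has a second alternative, and the grid schedules a C2/D1 evaluation. A site following the grid covers the full window for every patient who continues.
- The footnote times an assessment; 9.5.2 and SAP 3.2.4.1 define the window, and both say 28 days.
- Escalation under 7.1.3.2 waits until all patients at a level have completed Cycle 1. Nothing in the documents lets a cohort be called at Day 22.
- Late events have other routes. Presumed DLTs go to the sponsor within 24 hours of awareness (9.5.3). All AEs are recorded until the 1-Month Follow-up visit (9.2.1), at least 30 days after the last dose, so Day 45 or later if that dose was on Day 15.
- Toxicity may be front-loaded. One of the two DLTs at 9 mg/kg Q2W was an infusion-related reaction, and protocol 3.2.4.1 places these reactions mainly on Day 1. That makes a constant hazard doubtful.

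It could also be said that the infusion count in 9.5.2 is a minimum, so completing the period might require the full 28 days as well. The text does not say so, and the rule for the DLT Analysis Set does not test days of follow-up.

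What survives is the contradiction itself and the last row of the patient table. For that patient the AE data should exist, but no scheduled step turns them into a DLT answer after Day 22.

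**Conclusion.** Wrong as written; low severity. Footnote 5 in protocol Table 3 and in SAP 7.2 contradicts 8.2.3, 9.5.2 and SAP 3.2.4.1. At nominal dosing days the possible loss is 7 of 28 days (25%). It is confined to Q2W patients who have both Cycle 1 infusions, have no C2/D1 dosing visit, and are closed under the footnote's 7-day alternative.

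A reader might infer three stronger things that the documents do not support:

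- **That the Q2W window is shortened in general.** It is not: the C2/D1 evaluation restores it for anyone who continues.
- **That patients were in fact closed at Day 22.** No passage shows this for any patient.
- **That escalation decisions were distorted, for instance from 43% to 58%.** That figure is a ceiling. It needs all patients closed early, all later events missed despite AE reporting, and an assumed constant hazard.

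Enrollment stopped during Part 1 (SAP 1 and 4.14), so no future escalation depends on this. The remaining effect is on the accuracy of the reported DLT table and listing. The number of patients exposed cannot be worked out from the documents.

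**What to change.** 1. Reconcile footnote 5 of protocol Table 3 and footnote 5 of SAP 7.2 with protocol 8.2.3, protocol 9.5.2 and SAP 3.2.4.1, so that one closing rule for the Q2W DLT assessment appears throughout.
2. Before database lock, use the DLT assessment date on the CRF to list Q2W patients whose final assessment fell before C2/D1 or before the end of the 28-day window.
3. For those patients, check the AE records already collected, from that date to the end of the window, against the DLT criteria in 9.5.1. Settle any discrepancy at the Data Review Meeting (SAP 4.4.2) before Table 14.2.4.8 and Listing 16.2.7.1 are final. If the list is empty, one sentence in the study report closes the point.

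The cost is two footnote edits, one listing and a short medical review. No new visits or data are needed, because AE recording already runs past the end of the window.

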Pan-HER Infusion		X		X	X	X	X	X	X	X		X	X	X	X		
Post-Infusion Monitoring		X		X	X	X	X	X	X	X		X	X	X	X		

Abbreviations (in alphabetical order): ADA, anti-drug antibody; C, Cycle; CT, computed tomography; D/d, day(s); DLT, dose-limiting toxicity; EOT, End of Treatment; ECG, electrocardiogram; ECHO, echocardiogram; ECOG PS, Eastern Cooperative Oncology Group performance status; MRI, magnetic resonance imaging; MUGA, multi-gated acquisition; 1M FUP, 1-Month Follow-up; PK, pharmacokinetic; (S)AE, (serious) adverse event

Confidential Page 43 of 156

- 1) The treatment period continues until the patient is withdrawn from Pan-HER.
- 2) Applicable for Part 2 only: After the 1M FUP Visit, the Investigator will make every effort to obtain follow-up information on response assessment and/or OS every 2 months. Response assessment follow-up is required in the event of an ongoing SD, PR or CR at the 1M FUP Visit, until PD or another therapeutic intervention is initiated. Survival follow-up is required until death, withdrawal of consent, or termination of the trial. This continued follow-up does not require an in-person visit at the trial site, but may be obtained by collection of data/documentation.
- 3) Informed consent may be obtained outside the 14-day screening period prior to C1/D1, but is recommended to be obtained no earlier than 4 weeks prior to the planned C1/D1.
- 4) Screening assessments/baseline characteristics include demographics, medical history, tumor histology, mutation status, extent of disease, prior anti-cancer treatment etc.
- 5) DLT evaluation, Applicable for Part 1 only: DLTs are reported during Cycle 1 with final assessment 7 days after the last dose of Cycle 1 or prior to dosing on C2/D1.
- 6) Does not need to be performed on C1/D1 if performed during screening ≤ 7 days from C1/D1.
- 7) In addition to the scheduled timepoints, an ECG should be performed in the event of cardiac symptoms.
- 8) In addition to the scheduled timepoints, an ECHO/MUGA should be performed in the event of cardiac symptoms.
- 9) Local laboratory results must be available and assessed prior to each Pan-HER infusion for all infusions during Cycle 1, and for every second infusion from Cycle 2 onwards. Refer to Section 8.2.9 for further details
- 10) Complement sampling, Applicable for Part 2 only, will be done C1/D1 and in the event of an IRR. Refer to Section 8.2.10 for further details.
- 11) CT or MRI imaging schedule and conditions, applying to all cohorts:

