7.1.4.2 Dose-Delays for Pan-HER-Related or Disease-Related Toxicities

Clinical judgment will be used when determining whether it is advisable to continue a patient on to the next dosing. In order to dose a patient, the following retreatment criteria must be met. Evaluations must occur at minimum prior to each Cycle 1 dose and prior to D1 and D15 doses each cycle thereafter:

- 1. ANC $> 1.5 \times 10^9 / L (1500 / mm^3)$
- 2. Platelet count >75 $\times 10^9$ /L (75,000/mm³)
- 3. Any ongoing AEs should NOT meet the criteria for DLT, during the DLT-observation period
- 4. Any ongoing AEs, assessed as possibly, probably, or related to Pan-HER, should have either ameliorated to ≤ Grade 1 severity, returned to baseline status, or resolved with the exception of Grade 2 clinical events that are being adequately controlled with best supportive care (e.g., nausea, vomiting, diarrhea, fatigue) and asymptomatic laboratory abnormalities that are considered clinically insignificant or that are resolving with medical therapy

Should any one of the criteria above not be met, dosing of Pan-HER must be delayed until the patient meets the above criteria. All per protocol assessments must be done.

Confidential Page 64 of 156

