8.2.9 Laboratory Assessments and Pregnancy Test

All routine laboratory analyses will be performed at a laboratory facility local to the trial site.

Sponsor or designee must be provided with trial site laboratory normal ranges for all required parameters prior to screening of the first patient at the site. Likewise, any change in laboratory normal ranges during the trial should be forwarded to the Sponsor or designee promptly during the trial.

Blood samples will be taken at the scheduled visits and analyzed for the following parameters as per **Table 10** and as clinically indicated. Results must be available and assessed prior to dosing of Pan-HER, when sampling is scheduled on days of dosing. All individual assessments are to be performed on or about the indicated visit day (i.e., ± 2 days) unless otherwise stated.

Table 10 Schedule of Safety Blood and Urine Samples

Sample Analysis	Screening		Cycl	le 1		Cycles Thereafter		ЕОТ	1M FUP
Day within Cycle		D1	D3 D8	D15	D22	D1	D15		
Hematology Panel	X	X^1	X	X	X	X	X	X	X
Biochemistry Panel	X	X^1	X	X	X	X	X	X	X
Coagulation Panel	X	X^1		X		X		X	X
Urinalysis	X	X^1		X		X		X	X
Pregnancy Test	X							X	

Abbreviations (in alphabetical order): D, day; EOT, End of Treatment Visit; 1M FUP, 1-Month Follow-up Visit

1) Does not need to be performed prior to C1/D1, if performed during screening ≤7 days from C1/D1

Confidential Page 75 of 156

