8.2.9.1 Hematology Panel

To include complete blood count with differential, ANC, and platelet count.

- Screening
- Cycle 1
 - Weekly (prior to dosing if on dosing days)
 Note: Does not need to be performed prior to C1/D1, if performed during screening ≤7 days from C1/D1.
 - o Day 3
- Each cycle thereafter
 - o Day 1 and 15 (prior to dosing)
- EOT
- 1M FUP
- As clinically indicated

In the event of hematologic toxicity, the evaluation frequency should be increased to include additional evaluations between scheduled assessments, as clinically indicated.

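### On the Q2W schedule, Table 3 footnote 9 asks for laboratory results before only one of the two infusions per cycle from Cycle 2, in conflict with Protocol 7.1.4.2 and 8.2.9

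*Protocol*

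**What the plan says.** Four places in the protocol bear on this.

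- **Table 3 (Q2W), footnote 9**, attached to the safety blood and urinalysis rows. Results from the local laboratory must be ready and reviewed before the infusion "for all infusions during Cycle 1, and for every second infusion from Cycle 2 onwards". It then points the reader to Section 8.2.9. Footnote 9 of Table 2 (Q1W) has the same wording, and SAP Appendix 7.2 repeats the Q2W footnote.
- **Section 7.1.4.2**, the retreatment rule. Criteria 1 and 2 are ANC and platelet thresholds. On timing: "Evaluations must occur at minimum prior to each Cycle 1 dose and prior to D1 and D15 doses each cycle thereafter". On the consequence: "Should any one of the criteria above not be met, dosing of Pan-HER must be delayed until the patient meets the above criteria".
- **Section 8.2.9**, the general laboratory rule: "Results must be available and assessed prior to dosing of Pan-HER, when sampling is scheduled on days of dosing".
- **The sampling schedule.** After Cycle 1, the Table 3 grid, Table 10, 8.2.9.1 (hematology, which includes ANC and platelets) and 8.2.9.2 (biochemistry) all place samples on Days 1 and 15. The two panel sections specify that they are taken before dosing.

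**The concern.** A count of infusions means different things on the two schedules. With four infusions per cycle, every second one can be Day 1 and Day 15. With two per cycle, every second one is a single infusion. The footnote's wording is the same for both, so on Q2W it asks for less than the sections that govern dosing and laboratory review.

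What is at stake is the order of events on Day 15 of Cycle 2 and later. ANC and platelets decide whether a dose must be delayed, and 8.2.9.2 adds that clinically significant electrolyte abnormalities should be corrected before dosing. Both presuppose a known result. A site relying on the footnote could start the infusion while that result is pending.

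There is also a smaller data consequence. Such an infusion complies with the footnote but departs from 7.1.4.2 and 8.2.9. SAP 4.4.2 has every protocol deviation classed as minor or major, and major ones can remove a patient from an analysis set. SAP 4.11.2 summarizes treatment-emergent events that led to a dose reduction or delay. After Cycle 1, both could depend on which passage a site followed.

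**Working it through.** The plan states no figure here, so there is none to reproduce. The check is a count of infusions per 28-day cycle from Cycle 2 onward.

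**Inputs**
- Infusion days (Protocol 5.3, Table 1): Q1W on Days 1, 8, 15 and 22, so 4 per cycle; Q2W on Days 1 and 15, so 2 per cycle.
- Footnote 9: every second infusion.
- Section 7.1.4.2: Day 1 and Day 15 doses.
- Section 8.2.9 with Table 10: every dosing day on which a sample is scheduled. For hematology and biochemistry these are Days 1 and 15.

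**Share covered** = infusions needing a reviewed result before dosing ÷ infusions in the cycle.

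| Rule | Q1W | Q2W |
|---|---|---|
| Footnote 9 | 4 ÷ 2 = 2 of 4 (50%) | 2 ÷ 2 = 1 of 2 (50%) |
| 7.1.4.2 | 2 of 4 | 2 of 2 (100%) |
| 8.2.9 with Table 10 | 2 of 4 | 2 of 2 (100%) |
| Gap, footnote against the sections | 2 − 2 = 0 | 2 − 1 = 1 per cycle |

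The Q1W agreement assumes that counting starts at Day 1, so that every second infusion is Day 1 and Day 15. Those are also the later-cycle days marked for safety bloods in the Table 2 grid. On Q2W no starting point closes the gap: whichever infusion is counted first, one of the two in each cycle is left out. The footnote does not say which.

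**Cycle 1.** The footnote covers all Cycle 1 infusions and 7.1.4.2 covers each Cycle 1 dose, so there is no gap. The DLT observation period (9.5.2) is Cycle 1.

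**Sampling.** Under every passage a Q2W patient has hematology and biochemistry samples scheduled on both Day 1 and Day 15 of later cycles. The gap of one infusion per cycle therefore concerns when the result is reviewed, not whether blood is drawn.

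**The case against.** The best reply is that a careful reader would not be misled. The footnote refers onward to 8.2.9, which gives the fuller rule. It says when results are needed but does not itself permit dosing without them. Section 7.1.4.2 is the dosing rule and sets a minimum, and a site that follows it also satisfies the footnote. This is fair, and it limits the risk to a site that works from the schedule table alone. It does not remove the conflict: the cross-reference is offered for further detail, but it leads to a rule that differs from the footnote.

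One could also say that one infusion per cycle suits coagulation and urinalysis, which Table 10 schedules on Day 1 only after Cycle 1. That is true of those panels. But the footnote does not separate panels, and ANC and platelets belong to hematology, which is scheduled on both days.

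The practical reach is limited too. SAP Section 1 says enrollment was stopped during Part 1, and the SAP appendix does not direct dosing at sites. The drug-related events summarized in Protocol 3.2.4.1, from data not fully verified, include no neutropenia or thrombocytopenia. These points bear on how often the gap would matter. They do not settle which requirement applies to a patient still on treatment, or how a past Day 15 infusion should be classed.

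A reader might go further and infer several things that the documents do not support:

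- **That half of later Q2W infusions go ahead with no ANC or platelet test, or that monitoring falls to every 28 days.** The Day 15 sample is scheduled in every passage, so sampling stays at 14-day intervals.
- **That a patient who should be held will be dosed.** This happens only if the pending value turns out to fail a criterion, and no frequency is given.
- **That most current patients are exposed.** Protocol 3.2.4.1 gives 3 + 7 + 3 = 13 of 19 patients on Q2W, but these are patients entered by Amendment 6. At least one of the 13 had discontinued, and the number reaching Cycle 2 is not given.

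**Conclusion.** The conflict is real and specific to Q2W. From Cycle 2, footnote 9 covers 1 of 2 infusions per cycle, against 2 of 2 under 7.1.4.2 and under 8.2.9 with Table 10. The consequence is that a Day 1 or Day 15 infusion could start with the laboratory results that govern a dose delay still pending, if a site takes the footnote as its rule.

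This rests on two assumptions: that the footnote is read literally, and that patients are on the planned two-infusion cycle. The number of infusions actually affected cannot be derived from the documents.

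A reader might also infer that the primary endpoint or the escalation decisions are compromised. They are not: both rest on Cycle 1 DLTs, and the footnote requires results before every Cycle 1 infusion. Laboratory toxicity data come from the same scheduled samples under either reading. Only dosing, delay and deviation records after Cycle 1 could differ.

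The wording looks carried over from the Q1W table. Footnotes 5 and 15 of Table 3 also keep Q1W content: a 7-day final DLT assessment, where 8.2.3 gives 14 days for Q2W, and a reference to the Q1W PK table. The documents do not state the origin, and the conclusion does not depend on it.

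**What to change.** Reconcile footnote 9 of Protocol Table 3 with 7.1.4.2, 8.2.9 and Table 10, and make the same change in SAP Appendix 7.2. State the Q2W requirement in visit days and not as a count of infusions, so that every passage gives one answer to which infusions need reviewed results beforehand. If the requirement differs by laboratory panel, the footnote should say so. Which clinical rule applies is for the sponsor to decide; this point does not propose one. The Q1W footnote in Table 2 does not need to change for this reason.

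The cost is one protocol footnote and its SAP copy. Day 15 samples are already scheduled, so no visit or blood draw is added, and no planned analysis changes. If patients have already received later Q2W infusions, the data review meeting under SAP 4.4.2 should apply the reconciled requirement consistently when it classes any deviation of this kind.
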